in open fittings, REURs for the test ear will be measured as this data may facilitate refinement of correction factors. The test ear will be measured such that the appropriate slim tube/RIC receiver length and dome size prior to each fitting using manufacturer specific clinical tools and procedures. Each participant will be randomly assigned an audiogram for their open versus closed fittings. The audiograms selected for open versus closed coupling will be based on the fitting range of the device and that represent the configurations typically seen in open-fit hearing-aid users. The selected audiogram will be entered into the fitting software and Verifit, along with the average RECD for the test ear. The hearing aids will be programmed and verified to NAL-NL2 targets in the testbox. Because the instruments will be sealed in the coupler, initialization of feedback suppression processing will lead to erroneous results for open fitted instruments. Therefore, feedback suppression processing will be activated for all testing; however, the feedback initialization routine, which helps determine the maximum amount of stable gain on an individual ear, will not be run. After which, the output of the hearing aid will be measured in-situ with measured RECDs, and real ear aided responses (REUR) will be measured for all RICs and RITAs with both open and closed coupling for the assigned audiogram. It is estimated that each participant will require ~90 minutes of testing which will be completed in 1 session (with breaks).

Study 3.

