Study 2 Power Analysis. The sample size for this aim is based on having 12 monaural hearing aid fittings (3 manufacturers of 1 open RIC, 1 closed RIC, 1 open RITA, and 1 closed RITA) per participant (ears counterbalanced across participants such that odd-numbered subjects obtain fittings in the left ear and even numbered in the right ear). To ensure a wide range of RECDs and the expected variability in slit leak venting with closed domes, our target sample size is now 96 participants. See randomization Table in Appendix 6 in the grant application for details. For this single session study, we will account for 10% attrition due screen failure and thus will recruit an additional 10 participants for a total of N = 106.

Study 2 Data Analysis. The data from this study will not be analyzed in the usual manner as the purpose of this study is to develop correction factors for open and closed dome fittings of RIC and RITA style hearing aids from several manufacturers. First the frequency-specific gain deviations for each ear as a function of vent size will be calculated. Second, Linear and nonlinear modeling of these data with the goal of developing a best fit model of the relationship between physical vent size and the frequency specific change in gain. The model will also be adjusted as a function of hearing loss, if necessary, to account for cases when the model correction would erroneously lead to negative gain.

Study 3 Power Analysis. A power analysis based on the same expectations as Study 1 regarding fitting accuracy was conducted. For a mixed model repeated measure ANOVA with an effect size $\eta^2 = 0.10$, power $(1-\beta) = 0.80$, and $\alpha = 0.05$ requires a sample size of 100 ears (total of 50 participants) over the four groups, or 13 participants per group. A small effect size is expected, as a small effect size was found in the SPIRE data ($\eta^2 = 0.10$). Nonetheless, considering increased variability due to venting and to obtain robustness required by clinical standards, we will increase the sample size to achieve higher power of $(1-\beta) = 0.95$. This would bring the sample size of ears to 152, or 76 participants in total (19 per group). Considering 15% attrition, then 12 additional participants will be needed (N = 88) resulting in 22 participants per group.

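### Study 3 cites added venting variability as a reason for raising power to 0.95, but the 0.95 is computed at the unchanged effect size and holds no allowance for that variability

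*Combined protocol and SAP*

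**What the plan says.** All the sizing is in Data Analysis and Statistical Considerations, Study 3 Power Analysis.

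- Starting point: "A power analysis based on the same expectations as Study 1 regarding fitting accuracy was conducted". The effect size is eta-squared 0.10, attributed to the SPIRE data.
- Base case: "power $(1-\beta) = 0.80$, and $\alpha = 0.05$ requires a sample size of 100 ears (total of 50 participants) over the four groups".
- Reasons for going further: "considering increased variability due to venting and to obtain robustness required by clinical standards, we will increase the sample size to achieve higher power". The new target is 0.95.
- Result: "This would bring the sample size of ears to 152, or 76 participants in total (19 per group". An attrition allowance brings recruitment to 88.

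There are two reasons, venting variability and robustness. Neither is turned into an input: the plan states no larger SD, smaller eta-squared or variance inflation factor. The Study 3 Data Analysis section then says that left-ear and right-ear REAR data will be analysed separately, as in Study 1.

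**The concern.** Eta-squared is the share of total variance that the effect explains. If venting adds error variance while the difference in dB stays the same, eta-squared must fall. The paragraph expects more variability than lies behind the 0.10, yet keeps the 0.10. The stated 0.95 therefore describes the case in which the expected variability does not appear.

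What is at stake is how the design is described. A reader will take 0.95 as the power under the conditions the paragraph has just set out. The same extra ears can buy 0.95 at the old effect size, or some lower power with protection against more variability, but not both in full.

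**Working it through.** **Inputs from the plan:** eta-squared 0.10, alpha 0.05, four groups, 100 ears for 0.80, 152 ears for 0.95.

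**Not given:** the number of repeated measures, their correlation, and the size of the venting effect on variability.

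**Step 1. Reproduce the plan's figures.** Take a four-group F test with ears counted as the plan counts them.

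- f² = 0.10 / 0.90 = 0.111, so f = 0.333.
- Noncentrality λ = N × f², with 3 and N − 4 degrees of freedom.
- N = 100: λ = 11.11, power 0.790 (stated 0.80).
- N = 152: λ = 16.89, power 0.941 (stated 0.95).

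This test needs 103 and 159 ears for exactly 0.80 and 0.95, so 152 is slightly low on this method. A repeated-measures F test with assumed inputs (f = 0.10, seven measures, correlation 0.5) gives 100 and 152 ears exactly. Those inputs are a guess, and the conclusion does not depend on them. In both versions the effect size is the same for both targets.

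**Step 2. Does the step from 100 to 152 leave room for a smaller effect?** The plan's ratio is 152 / 100 = 1.52. At a fixed effect size the F test needs 159 / 103 = 1.54. The change of target uses up the whole increase.

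**Step 3. Add variability.** Let the SD be k times larger with the mean differences unchanged. Then f² becomes 0.111 / k², λ becomes 152 × 0.111 / k², and eta-squared becomes f² / (1 + f²). The values of k are assumed.

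| SD increase | Eta-squared | λ, 152 ears | Power, 152 ears |
|---|---|---|---|
| 0% | 0.100 | 16.89 | 0.941 |
| 10% | 0.084 | 13.96 | 0.886 |
| 20% | 0.072 | 11.73 | 0.820 |
| 23% | 0.069 | 11.19 | 0.80 |
| 30% | 0.062 | 9.99 | 0.748 |
| 50% | 0.047 | 7.51 | 0.610 |

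The break-even is k = 1.228, or error variance up by about 51% (1.228² = 1.51). The repeated-measures version breaks even at an SD increase of about 25%.

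**Step 4. The analysis actually planned.** Separate left-ear and right-ear models have 76 ears each, not 152. The same F test on 76 ears (λ = 76 × 0.111 = 8.44) gives 0.65 with no added variability, and 0.56, 0.48 and 0.42 with SD 10%, 20% and 30% higher. The unit of analysis is a separate matter from venting. It does mean that the 152-ear column should not be copied into the protocol as the power of the planned models. The 76-ear figures are also only a guide, because the plan specifies a mixed-model repeated-measures ANOVA with inputs it does not state.

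**The case against.** The best defence is that the arithmetic is sound and the extra ears are a safety margin: oversize at the nominal effect so that power stays acceptable if variability turns out higher. That is a fair reading, and on the plan's count the margin works up to an SD increase of about 23%. The plan does not say in so many words that 0.95 holds under inflated variability, and it gives robustness as a second reason. It is also unknown whether the SPIRE data already included vented or open fittings, so the amount still to be added cannot be worked out.

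All of this limits the point without removing it. The margin reading is not written down: no tolerated inflation is named, and 0.95 is given without a condition.

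A reader might go further in three ways, none of which the documents support.

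- That 152 is a miscalculation. It reproduces closely at eta-squared 0.10.
- That venting takes the study below 0.80. No inflation is stated, so this is not shown on the plan's count.
- That the overstated power is what would lead a null comparison of experimental with standard-of-care fittings to be over-read. That risk comes from seeking equivalence through difference tests with no margin, and it would remain at a true 0.95.

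**Conclusion.** The point holds in a limited form. The 152 ears give about 0.95 at the unchanged eta-squared of 0.10, so any added variability, with the same dB difference, puts power below 0.95. The direction is certain. The size is not, because it depends on an inflation that the plan does not state. Over an assumed SD increase of 10% to 30%, power on the plan's count runs from 0.89 down to 0.75, crossing 0.80 at about 23%. These figures rest on a four-group F test with 152 ears treated as independent. The defect is an unconditional power statement that conflicts with its own stated reason.

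**What to change.** In the Study 3 Power Analysis:

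1. State that 0.95 is the power at eta-squared 0.10 and includes no allowance for venting variability.
2. Then do one of two things. Either state the assumed variance inflation (or reduced eta-squared) and report the power that results, or describe the extra ears as a margin that keeps power at 0.80 up to a named inflation.
3. Compute the restated figure for the separate left-ear and right-ear models with 76 ears each, giving the number of repeated measures and the correlation. If the margin option is chosen, check it on that basis too, since the 23% margin belongs to the 152-ear count.

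Study 2 measures in situ responses with both open and closed coupling and could inform the variance. The raw SD of in situ minus testbox output should not be used. Those fittings use simulated audiograms and an average RECD, and are made before the correction factors exist. Use the residual SD after the correction model is applied, by coupling, and only for the experimental arms. Standard-of-care fittings are matched to target in the ear, so their variance needs its own stated assumption.

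The cost is a few sentences, one recalculation and, if Study 2 is used, one variance estimate from data already planned. N need not change. The downside is a less favourable stated power.

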Study 1 Power Analysis. The primary outcome of interest is based on fitting accuracy of each ear (i.e., deviation of REAR from prescriptive target across frequency). A power analysis for a repeated measure ANOVA with an effect size $\eta^2 = 0.10$, power ($1-\beta$) = 0.80, and $\alpha = 0.05$ requires a sample size of 100 ears (total of 50 participants) over the two groups. A small effect size is expected, as a small effect size was found in the preliminary data ($\eta^2 = 0.10$). Considering 15% attrition, then 8 additional participants will be needed ($N = 58$) resulting in 29 participants per group.

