Study 1 Data Analysis Plan. A generalized linear model will be applied to examine fitting accuracy. This analysis will examine differences (in dB SPL) for in situ REAR (based on testbox fittings) across frequency between the groups relative to the prescription. Because it is expected that differences within the two ears of the same subject will be smaller than differences across subjects, inclusion of both ears in the same analysis may over inflate the statistical power. However, it is also of interest to ensure that all data are considered. Therefore, we propose to complete separate analyses for the left and right ear, even though we expect the pattern of results to be very similar for each ear. These analyses will determine (1) in situ REARs of the testbox fittings matched the prescription within each group, and (2) if there was an effect of fitting accuracy as a function of style. A generalized linear model will be conducted to compare the expected (from prescription) and actual aided SII within and between groups. Finally, separate mixed model repeated measures ANOVA will be applied to examine group differences among the outcome measure subscales (i.e., SADL subscales, IOI-HA items/subscales, and for the APHAB subscales) to examine differences in outcomes between groups and between current hearing aid fittings and the replacement testbox fittings. For the COSI, the percentage of 'better' and 'much better' responses and the average of the final ability will be calculated across goals and compared between groups via a paired-sample t-test. The subjective outcomes of replacement hearing aids (Session 3) from testbox fittings will also be compared to normative data for each group by comparing our mean, standard deviation, and sample size to those same variables from the published outcome respectively via a Welch test. This will inform whether our outcomes for testbox fittings of replacement hearing aids from each group were consistent with the published norms or not. For the IOI-HA, the IOI-HA norms from the VA ROES DALC database that contains over 100,000 IOI-HA records will be used. In the same fashion, we can select IOI-HA norms from ROES by based on degree of hearing loss and hearing aid style. A

logistic regression also will be conducted to examine if the proportion of responses differ between the groups on the specific telephone and exit survey items of interest.

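### Studies 1 and 3 count two ears per participant to reach their REAR sample sizes but analyse left and right ears separately, so the stated power is not demonstrated for the planned tests

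*Combined protocol and SAP*

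**What the plan says.** Under Study 1 Power Analysis, "The primary outcome of interest is based on fitting accuracy of each ear", meaning the deviation of REAR from target across frequency. For a repeated-measures ANOVA with eta-squared 0.10, power 0.80 and alpha 0.05, the plan "requires a sample size of 100 ears (total of 50 participants) over the two groups". Allowing for 15% attrition, the enrolment target is 58.

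Study 3 Power Analysis starts from the same expectations and the same 100 ears, now spread over four groups. It then raises power to 0.95: "This would bring the sample size of ears to 152, or 76 participants in total (19 per group", with 88 to be enrolled.

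Study 1 Data Analysis Plan takes a different unit. It expects the two ears of one person to be more alike than ears of different people, and warns that "inclusion of both ears in the same analysis may over inflate the statistical power". For that reason "we propose to complete separate analyses for the left and right ear". The plan chooses this split although its authors anticipate closely matching findings in the two ears. Study 3 Data Analysis adopts the same split for its REAR data.

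Two different terms are described for the Study 1 comparison. One is differences "across frequency between the groups relative to the prescription"; the other is "if there was an effect of fitting accuracy as a function of style". The Design section says that each experimental group in Study 3 is compared with its own standard-of-care (SoC) group, open with open and closed with closed.

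**The concern.** The divisions are right: 100/2 = 50 and 152/2 = 76. The difficulty is that the power sections and the analysis sections use different units. A requirement stated in ears is met by counting both ears of each participant. Each planned REAR test then uses only one ear of each participant, so it runs on half the units said to be needed. The plan's own reason for splitting the ears is that counting both would overstate power, yet the sample sizes were not restated to match.

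REAR accuracy is the stated primary outcome of Study 1 and the basis of the Study 3 sample size. A reader would credit each left-ear or right-ear test with power 0.80 or 0.95, and would read a non-significant group difference with that assurance. The plan supports those figures only for twice as many units. It also gives no rule for the case where the left and right analyses disagree.

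The point concerns the between-group REAR difference tests, which are what the stated power covers. The within-group match to prescription is also run by ear in both studies, but no power is stated for it. Study 3's equivalence claim and the self-report outcomes are outside this point.

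**Working it through.** **Inputs from the plan.** Eta-squared 0.10; alpha 0.05; two groups in Study 1 and four in Study 3; 100 ears for power 0.80; 152 ears for power 0.95; 50 and 76 completers; 58 and 88 enrolled.

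**Inputs the plan does not give.** The tested term, whether 0.10 is a partial value for that term, the number of frequencies, their correlation, and the correlation between ears. Values used for these below are assumptions.

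**Formula.** f² = 0.10/(1 − 0.10) = 0.111. For a between-group F test with one value per unit, the noncentrality is λ = N × f², with k − 1 and N − k degrees of freedom, where k is the number of groups.

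**1. The plan's own figures, with ears treated as independent and one value per ear.**
- Study 3, 100 ears, four groups: λ = 11.11, power 0.790 (103 ears needed for 0.80).
- Study 3, 152 ears, four groups: λ = 16.89, power 0.941 (159 ears needed for 0.95).
- Study 1, 100 ears, two groups: λ = 11.11, power 0.910 (73 ears needed for 0.80).

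The Study 3 powers come close, which is consistent with ears having been counted as independent units there but does not prove it. Study 1's 100 ears do not reproduce this way. The exact repeated-measures calculation cannot be rerun without the missing inputs.

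**2. The same test with one ear per participant.**

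| Test | N | λ | Power | Stated |
|---|---|---|---|---|
| Study 1, two groups | 50 | 5.56 | 0.64 | 0.80 |
| Study 3, four groups | 76 | 8.44 | 0.65 | 0.95 |
| Study 3, one matched contrast (19 v 19) | 38 | 4.22 | 0.52 | none stated |

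The last row takes 0.10 as the effect for that contrast itself. If nobody dropped out, the first two rows would be 0.70 (N = 58) and 0.73 (N = 88).

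**3. The same group test averaged over frequencies.** With m frequencies at common correlation r, λ = N × f² × m/(1 + (m − 1)r). For an assumed m = 10 and r = 0.4, the multiplier is 10/4.6 = 2.174.
- Study 1, N = 50: λ = 12.08, power 0.93.
- Study 3, four groups, N = 76: λ = 18.36, power 0.95.

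Under this setting 35 ears would be enough for 0.80 in Study 1, and 76 for 0.95 in Study 3. The stated 100 and 152 would then not be the requirement.

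The result depends on r. At r = 0.6 the multiplier is 10/6.4 = 1.563, and power is 0.82 in Study 1 and 0.86 in Study 3. At r = 0.8 it is 10/8.2 = 1.220, and power is 0.72 and 0.75.

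**4. The group-by-frequency term.** Take 0.10 as the partial value for this term, with sphericity and 3 to 7 frequencies assumed. Then λ = f² × (N − k)(m − 1), with (k − 1)(m − 1) and (N − k)(m − 1) degrees of freedom. One ear per participant gives 0.83 to 0.995 in Study 1 and 0.85 to 0.998 in Study 3, where 0.95 is reached only from 5 frequencies.

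**The case against.** The strongest reply is that the plan specifies a repeated-measures ANOVA on an outcome defined across frequency, so one value per ear is not the stated design. Steps 3 and 4 bear this out: under plausible settings, 50 and 76 single ears reach or exceed the stated power. One setting (10 frequencies, correlation 0.4) does so for both studies. This part of the reply stands. A reader might infer from the 0.64 and 0.65 that the studies are underpowered, and the documents do not support that. They also do not support the opposite inference, since they state none of the inputs on which the favourable result rests and it weakens as the correlation rises. If the favourable setting is what was meant, the ear counts presented as required are themselves wrong.

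It is also fair to say that the ear split is deliberate and disclosed, and that it prevents the two ears of one person from being tested as if they were independent. That defends the analysis but leaves the power statement unmatched to it. The 15% allowance does not close the gap either, because it covers dropout.

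Finally, the named hypotheses concern accuracy against target and, in Study 3, equivalence to SoC. The between-group difference tests are only part of what these studies set out to show. That limits the weight of the point and is one reason to rank it below a must-fix.

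**Conclusion.** The mismatch in the unit of analysis is certain: each planned left-ear or right-ear REAR test has 50 units in Study 1 and 76 in Study 3, against stated requirements of 100 and 152. The stated power of 0.80 and 0.95 is therefore not demonstrated for the between-group tests.

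The size of any shortfall is not known. With eta-squared 0.10, alpha 0.05 and the planned completers, it runs from none (10 frequencies at correlation 0.4, or a group-by-frequency term with 5 or more frequencies) to a power of about 0.64 to 0.65 (one value per ear). For a single matched contrast analysed with one value per ear, power is 0.52. This is a sample-size and unit-of-analysis inconsistency that should be fixed. It is neither an arithmetic slip nor proof of an undersized trial.

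**What to change.** Restate the power for Studies 1 and 3 for the REAR analysis as planned, with one ear per participant and 50 and 76 completers. The restatement should give:
- the tested term or contrast, including EXP-open v SoC-open and EXP-closed v SoC-closed;
- whether eta-squared 0.10 is a partial value for that term;
- the assumed number of frequencies and their correlation;
- what will be concluded if the left and right results disagree.

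An equally acceptable route is one mixed model per study with both ears, a random participant effect and frequency as a repeated factor. Power would then be restated with the participant as the cluster and a stated inter-ear correlation ρ. As a guide, take one value per ear, λ = f² × 2n/(1 + ρ) for n participants, and error degrees of freedom counted from participants. For ρ from 0.5 to 0.9, power is 0.76 to 0.66 in Study 1, 0.79 to 0.68 for four groups in Study 3, and 0.64 to 0.54 for one 19 v 19 contrast. The gain over a single ear is small if the ears are as alike as the plan expects.

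Either route costs wording and a recalculation, with no extra participants or data. The downside is that the restated power may be less favourable than the present figures.

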PROTOCOL TITLE: Efficacy of a Coupler-Based Fitting Approach for Experienced Users Receiving Replacement Hearing Aids

PRINCIPAL INVESTIGATOR: [name], Au.D., Ph.D.

VERSION NUMBER AND DATE: Version 10, June 10, 2022

SPONSOR/FUNDING SOURCE: VA RR&D Merit Review C2777-R

Purpose

The overarching purpose of this project is to develop an accurate coupler-based fitting model for experienced hearing-aid users obtaining replacement hearing aids of any style that will result in positive patient outcomes while mitigating a face-to-face fitting visit.

The proposed project addresses three aims:

Specific Aim 1. Develop vent correction factors for testbox fittings of in-the-ear (ITE) and traditional behind the ear (BTE) with custom earmold hearing aids, which will be used to evaluate the real ear to complete difference (RECD)-fitting approach in a sample of experienced users receiving replacement hearing aids. Hypothesis 1a. RECD coupler-based fittings will accurately meet prescriptive targets and expected aided audibility for ITE and traditional BTE styles. Hypothesis 1b. Subjective outcomes from RECD coupler-based fittings will meet or exceed published norms.

Specific Aim 2. Develop correction factors for RECD coupler-based fittings of hearing aids with non-custom coupling (i.e., mini-BTEs with slim tubing and noncustom open canal coupling—open fits). Hypothesis 2. Correction factors will be developed to account for RECD coupler-based fittings with open canals.

Specific Aim 3. To determine if the open-fit RECD-fitting approach is equivalent to the standard of care (SoC) open-fit fitting approach. Hypothesis 3a. Derived REARs from open-fit RECD-fittings will accurately meet prescriptive targets and expected aided audibility and will be equivalent to in situ REARs in SoC fittings of open-fit styles. Hypothesis 3b. The subjective outcomes will not significantly differ between the experimental RECD-fitting group and the SoC group for open-fit styles.

Background and Significance

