Study 3 will use a quasi-random design. Participants receiving replacement receiver in the canal (RIC) mini BTE hearing aids and will be randomly assigned to one of four groups based on hearing-aid coupling (open vs closed domes). The standard of care (SoC) group receiving open coupling (SoC-open) or closed coupling (SoC-closed) or the experimental group receiving the experimental (EXP) hearing aid service delivery approach (EXP-open or EXP-closed). The outcomes of the experimental fittings will be compared to the respective SoC fitting.

Risk/Benefit Assessment

The procedures used in the proposed study produce minimal risks. There are no known social, legal, physical, psychological, genetic or financial risks associated with participation. All participants in Study 1 or Study 3 will receive a standard, comprehensive hearing evaluation. Some participants may find this boring or may be frustrated when repeated words that might be difficult to hear or listen for soft beeps. This is a common clinical procedure that is not invasive. All participants in Study 1 or Study 3 will obtain a cognitive screening test. This screener may cause people to feel uncomfortable having to be asked to remember things or if they find the test difficult. All participants will receive in situ real-ear verification of hearing aid fitting(s). There may be slight discomfort during these measurements, but they should not be painful and they are routine, taking only a few minutes to complete for each ear.

Participants in Study 1 only will have earmold impressions made of their ears so custom replacement behind-the-ear and in-the-ear hearing aids can be ordered for each ear. There is a rare, but small chance of ear injury during this routine clinical procedure. All standard clinical safeguards associated with obtaining earmold impressions (otoscopy, use of otoblocks) will be used.

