Session 1 (Baseline, Pre-Fitting). The baseline testing for Session 1 of Study 3 is nearly identical to the procedures in Session 1 of Study 1. See Section 3g. Thus, only the minor differences will be described here. The comprehensive hearing evaluation, completion of the intake form (Appendix), and reorientation that is needed will be completed with the participant's current hearing aids. Their current hearing aids will be maintained and re-verified to ensure an accurate fit to prescriptive targets. The self-report outcome battery on the current hearing aids will be assessed (COSI, SADL, IOI-HA, and the aided portion 1 of the APHAB). Individual RECDs and REURs will be measured for each ear of each participant. The choice in replacement open vs closed domes will be made following routine clinical procedures. The receiver length will be measured and the dome size (open vs closed) will be estimated using manufacturer measurement tools. The replacement hearing aids will be ordered in ROES.

Session 2-The Intervention 'Visit'.

SoC-open and SOC-closed Group Fittings. These groups will receive the SoC, 30-minute face-to-face fitting appointment 4 weeks after Session 1, the average wait time for a fitting appointment. The right and left hearing aids will be programmed separately to the National Acoustics Laboratory Non-Linear 2 (NAL-NL2) prescription. The REAR of the hearing aids will be verified to the 50-, 65-, and 75-dB SPL prescriptive targets generated by the Verifit 2 system using the Speechmap™ stimulus. The criterion for an appropriate fitting would be ± 3 dB between the output and the prescriptive target from 250 Hz to the frequency in which the unaided threshold crossed the 65-dB SPL target. The real ear aided response for an 85 dB SPL input (REAR85) will be measured using an 85-dB SPL swept pure-tone to ensure that the maximum output of the hearing aids does not exceed the predicted uncomfortable loudness levels of the participant (feedback manager deactivated during this measurement only). The programming options will be optimized based on the information obtained on the intake form (Appendix). The participant will be provided with the manufacturer brochure and programming report from the manufacturer software. Consistent with current SoC, no orientation will be provided.

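### Study 3's stated power of 0.95 counts 152 ears as independent units in a four-group test; the planned per-ear and within-dome comparisons have less, about 0.65 and 0.52 on the plan's effect size

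*Combined protocol and SAP*

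**What the plan says.** - **Aim.** Under Purpose, Specific Aim 3 is "To determine if the open-fit RECD-fitting approach is equivalent to the standard of care (SoC) open-fit fitting approach". Hypothesis 3a expects equivalent real-ear aided responses (REARs); Hypothesis 3b expects no significant difference in subjective outcomes.
- **Design, Study 3.** Participants "will be randomly assigned to one of four groups based on hearing-aid coupling": SoC-open, SoC-closed, EXP-open and EXP-closed. On the comparison: "The outcomes of the experimental fittings will be compared to the respective SoC fitting".
- **Study Interventions, Study 3, Session 1.** "The choice in replacement open vs closed domes will be made following routine clinical procedures".
- **Study 3 Power Analysis.** A mixed-model repeated-measures ANOVA with eta-squared 0.10 and power 0.80 "and $\alpha = 0.05$ requires a sample size of 100 ears (total of 50 participants) over the four groups, or 13 participants per group". The target is then raised to 0.95: "This would bring the sample size of ears to 152, or 76 participants in total (19 per group"). Allowing for attrition, 88 are enrolled, 22 per group.
- **Study 3 Data Analysis.** Left and right REAR data are analysed separately, as in Study 1. The Study 1 Data Analysis Plan gives the reason: putting both ears in one analysis may overstate power.

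**The concern.** The sample size is justified on one unit and one test, while the analysis uses another unit and, for the comparison named in the Design section, another test. Two ears of one person are not two independent observations, and the plan says so itself. A four-group omnibus test also does not address whether EXP-open differs from SoC-open, which involves half the participants.

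A reader who trusts 0.95 would take a non-significant open-fit result as strong reassurance. If power for that contrast is nearer one half, the same result says little. The risk is greater because the aim is worded as equivalence while the planned tests look for differences.

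The two statements on dome assignment raise a second question: which contrasts are randomised, and whether 19 open-fit participants per arm can be counted on.

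**Working it through.** **Inputs from the plan.** Eta-squared 0.10; alpha 0.05; 152 ears, 76 participants, 19 per group; four groups. **Assumed here.** Two-sided pairwise tests, the inter-ear correlations, and that eta-squared 0.10 carries over to a two-group contrast.

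**1. Effect size.** f² = 0.10/0.90 = 0.111, so f = 0.333. For two equal groups d = 2f = 0.667.

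**2. The plan's own figure.** One-way F test, noncentrality λ = N·f².
- N = 152, four groups (df 3, 148): λ = 16.89, power **0.941** (stated 0.95).
- N = 100, four groups: λ = 11.11, power **0.790** (stated 0.80).

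Other variants do not fit at N = 152: a one-degree-of-freedom effect gives 0.983, f = √0.10 gives 0.913, f = 0.25 gives 0.725. Repeated-measures versions with 2 to 8 measurements and correlations of 0 to 0.7 matched neither stated figure.

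**3. Same test, one ear per person.** N = 76 (df 3, 72): λ = 8.44, power **0.654**. Averaging both ears with inter-ear correlation ρ gives λ = 152·f²/(1+ρ): 0.79 at ρ = 0.5 and 0.68 at ρ = 0.9.

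**4. EXP v SoC.** Two-sample t test, noncentrality d·√(n/2), with d = 0.667; for the mean of both ears, d/√((1+ρ)/2).

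| Contrast | One ear | Both ears, ρ = 0.9 to 0.5 |
|---|---|---|
| Open fits, 19 v 19 | **0.52** | 0.54 to 0.64 |
| Open fits, 22 v 22 (no attrition) | 0.58 | not computed |
| Both dome types, 38 v 38 | **0.82** | 0.84 to 0.91 |

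With 19 v 19, even ρ = 0 gives only 0.81. At d = 0.667 a pair needs about 37 per group for 0.80 and 60 per group for 0.95.

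**5. Sensitivity to d.** A four-group eta-squared does not fix the open-fit difference. With 19 v 19, d = 0.5, 0.667, 0.8 and 0.943 give 0.32, 0.52, 0.67 and 0.81. The last value, f·√8, is the largest pairwise d if the other two groups sit midway.

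**6. Repeated frequencies.** If eta-squared 0.10 applied at each frequency, m frequencies with correlation r would multiply λ by m/(1+(m−1)r). For m = 4 to 8 and r = 0.7 to 0.3 (assumed), the open-fit pair would have 0.62 to 0.89 and the four-group test on 76 units 0.78 to 0.98. The 152-ear calculation would then exceed 0.98, so this is not how 0.95 arose.

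**7. Dome numbers.** If clinical choice yields 11, 15, 23 or 27 open-fit participants per arm, power at d = 0.667 is 0.32, 0.42, 0.60 or 0.67.

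**The case against.** - **The aim is equivalence.** A reader might infer that Aim 3 itself has power 0.52. The documents do not support that: 0.52 is power to detect a difference, and no margin or SD is given. This stands, and it applies equally to the 0.95. As illustration only, with an assumed 3 dB margin, no true difference and 19 v 19, two one-sided tests have power 0.83, 0.47 or 0.15 for an SD of 3, 4 or 5 dB.
- **Dome type and randomisation.** A reader might also infer that the power calculation treats dome type as randomised. The Study 3 Power Analysis says nothing on allocation, and the F-test figure does not depend on it. The Design section calls the design quasi-random and can be read as fixing coupling first and then assigning SoC or EXP. The text is ambiguous and needs reconciling; no error in allocation is shown.
- **Open-fit may cover both domes.** Aim 2 uses the term for non-custom coupling generally, and Study 2 implements it with open and closed domes. On that reading 38 v 38 applies. The Design section's pairing of each EXP group with its own SoC group points the other way. Both figures should therefore be stated.
- **Effect size and model.** The plan does not say which effect eta-squared describes, and the formula above gives 0.91, not 0.80, for Study 1's 100 ears in two groups. This stands as a reason to give ranges. With favourable repeated-measures assumptions the four-group per-ear test could reach 0.95, but the plan states none, and the open-fit pair stayed below 0.95 in every case tried.
- **Confounding.** The Design section already compares within dome type, and nothing commits the sponsor to drawing Aim 3 from an undifferentiated four-group test. That largely answers the worry that ear type would drive the Aim 3 result.

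**Conclusion.** The concern holds for the stated power. The 0.95 belongs to a four-group test on 152 independent ears, a unit that the plan's own analysis section sets aside. With one ear per participant that test has about 0.65 (0.68 to 0.79 using both ears). The open-fit EXP v SoC contrast has about 0.52, with a range of 0.32 to 0.81 over the values of d considered; EXP v SoC over both dome types has about 0.82.

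These are one-way, between-group powers to detect a difference. They rest on eta-squared 0.10 carrying over to each contrast and take no credit for repeated frequencies. None of them is the power for equivalence.

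The allocation wording is a separate, lesser point: the Design and Session 1 statements need to be reconciled, and until they are, 19 open-fit participants per arm is not assured.

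**What to change.** 1. **Power.** Withdraw the 0.95. Restate power with the participant as the unit: about 0.65 for the four-group test, about 0.52 with its range for open-fit EXP v SoC, and about 0.82 for EXP v SoC stratified by dome type. Label all three as power to detect a difference. If credit is claimed for repeated frequencies or both ears, state the number of measurements and the assumed correlations.
2. **Interpretation.** State that a non-significant open-fit result will not be read as equivalence.
3. **Allocation.** Reconcile the Design and Session 1 statements. If the dome is chosen clinically, say that randomisation to EXP or SoC is within dome type, analyse EXP minus SoC with dome type as a stratum, report the open-fit and closed-fit contrasts separately, and describe open v closed as non-randomised. Whether the stratified or the open-fit contrast is primary is the sponsor's choice: the first has more power, the second is closer to the wording of Aim 3.

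The cost is protocol and analysis-plan wording and a less favourable stated power. No extra participants are needed.
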